- c. This blood collection is only applicable to subjects consenting to PBMC collection at designated PBMC sites.

Table 2 Primary Study Cohort - Stage 2 Schedule of Activities is applicable to Stage 1 subjects who are invited and consent to revaccination at Month 12. Study procedures for this cohort are fully described in [Section 6.2](#).

Table 2. Schedule of Activities: Primary Study Cohort - Stage 2						
Visit Number	5^a	6A^b	6	7	8	9
Visit Description	Vaccination 2	1-Week Revaccination Follow-up Visit	1-Month Revaccination Follow-up Visit	3-Month Revaccination Follow-up Visit	6-Month Revaccination Follow-up Visit	12-Month Revaccination Follow-up Visit
Study Period	Month 12		Month 13	Month 15	Month 18	Month 24
Visit Window (Days)	300 to 400 Days after Visit 1	6 to 8 Days After Visit 5	28 to 35 Days After Visit 5	84 to 105 Days After Visit 5	168 to 210 Days After Visit 5	350 to 378 Days After Visit 5
Confirm/obtain informed consent for Stage 2 ^c	X					
Perform physical examination, vital signs (weight, oral temperature, heart rate, and seated blood pressure)	X					
Review inclusion/exclusion criteria	X					
Record nonstudy vaccine information	X	X	X	X	X	X
Review temporary delay criteria	X					
Confirm understanding and compliance with protocol requirements for contraception (male subjects)	X	X	X			
Obtain IP container number	X					
Collect blood sample for antibody assessment	~25 mL		~25 mL	~25 mL	~25 mL	~25 mL
Collect blood sample for cellular assay ^d	~100 mL	~50 mL	~50 mL		~50 mL	
Administer investigational product in left deltoid muscle and SIIV in right deltoid muscle	X					
Assess acute reactions for at least 30 minutes after investigational product administration	X					
Provide subject with 14-day e-diary, thermometer, and measuring device	X					
Review e-diary data (daily review is optimal)	-----X-----					

Table 2. Schedule of Activities: Primary Study Cohort - Stage 2

Visit Number	5 ^a	6A ^b	6	7	8	9
Visit Description	Vaccination 2	1-Week Revaccination Follow-up Visit	1-Month Revaccination Follow-up Visit	3-Month Revaccination Follow-up Visit	6-Month Revaccination Follow-up Visit	12-Month Revaccination Follow-up Visit
Study Period	Month 12		Month 13	Month 15	Month 18	Month 24
Visit Window (Days)	300 to 400 Days after Visit 1	6 to 8 Days After Visit 5	28 to 35 Days After Visit 5	84 to 105 Days After Visit 5	168 to 210 Days After Visit 5	350 to 378 Days After Visit 5
during the active diary period)	14 days					

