Review and collect e-diary			X			
Record AEs, medically attended AEs, AEs of specific interest, and SAEs as appropriate	X	X	X	X	X	X

Abbreviations: e-diary = electronic diary; SIIV = seasonal inactivated influenza vaccine; PBMC = peripheral blood mononuclear cell.

- a. This Visit 5 schedule applies to subjects invited and consenting to revaccination at Month 12.
- b. Visit 6A is only applicable to subjects consenting to PBMC collection at designated PBMC sites.
- c. Consent may be obtained prior to Visit 5.
- d. This blood collection is only applicable subjects consenting to PBMC collection at designated PBMC sites.

Table 3 Schedule of Activities is applicable to subjects participating in the RSV Vaccine Month-0, Month-2 Cohort. Study procedures for this cohort are fully described in [Section 6.3](#).

Table 3. Schedule of Activities: RSV Vaccine Month-0, Month-2 Cohort

Visit Number	1	2A ^a	2	3	4A ^a	4	5	6
Visit Description	Vaccination 1	1-Week Post-Vaccination 1 Follow-up Visit	1-Month Post-Vaccination 1 Follow-up Visit	Vaccination 2	1-Week Post-Vaccination 2 Visit	1-Month Post-Vaccination 2 Visit	6-Month Post-Vaccination 2 Visit	12-Month Post-Vaccination 2 Visit
Study Period	Month 0		Month 1	Month 2		Month 3	Month 8	Month 14
Visit Window (Days)	Day 1	6 to 8 Days After Visit 1	28 to 35 Days After Visit 1	54 to 66 Days After Visit 1	6 to 8 Days After Visit 3	28 to 35 Days After Visit 3	168 to 210 Days After Visit 3	350 to 378 Days After Visit 3
Obtain informed consent	X							
Assign subject number	X							
Obtain demography and medical history data	X							
Assess tobacco usage	X							
Document medications currently taken	X							
Perform physical examination, including vital signs (weight, height, oral temperature, heart rate, and seated blood pressure)	X							
Record nonstudy vaccine information	X	X	X	X	X	X	X	X
Confirm eligibility	X							
Review temporary delay criteria	X			X				
Confirm understanding of and compliance with protocol requirements for contraception (male subjects only)	X	X	X	X	X	X		
Assign randomization number	X							
Collect blood sample for antibody	~25 mL		~25 mL	~25 mL		~25 mL	~25 mL	~25 mL

Table 3. Schedule of Activities: RSV Vaccine Month-0, Month-2 Cohort

Visit Number	1	2A ^a	2	3	4A ^a	4	5	6

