4.3. Criteria for Temporarily Delaying Vaccine Administration

The following conditions are temporary or self-limiting and a subject may be vaccinated once the condition(s) has/have resolved and no other exclusion criteria are met.

- Current febrile illness (oral temperature $\geq 100.4^{\circ}\text{F}$ [$\geq 38^{\circ}\text{C}$]) or other acute illness within 48 hours before investigational product administration.
- Any acute respiratory illness within 14 days before investigational product administration.

- Receipt of any inactivated vaccine within 14 days or any live vaccine within 28 days before or anticipated receipt of any vaccine within the 14 days after investigational product administration.
- Receipt of short-term (<14 days) systemic corticosteroids. Investigational product administration should be delayed until systemic corticosteroid use has been discontinued for at least 28 days. Inhaled/nebulized, intra-articular, intrabursal, or topical (epidural, skin, or eyes) corticosteroids are permitted.

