Before any study-related procedures are performed, voluntary, written study-specific informed consent for the revaccination stage will be obtained from the subject. Each signature on the ICD must be personally dated by the signatory. The investigator or his or her designee will also sign the Primary Study Cohort - Stage 2 ICD. A copy of this signed and dated ICD must be given to the subject. The source data must reflect that this informed consent was obtained before participation in the second stage of this study. Ideally, informed consent will be obtained prior to this visit.

It is anticipated that the procedures below will be conducted in a stepwise manner. Ensure that the procedures listed prior to administration of the vaccine are conducted prior to vaccination.

- Perform physical examination including vital signs (weight, oral temperature, heart rate, and seated blood pressure), evaluating any clinically significant abnormalities within the following body systems: general appearance; skin; head, eyes, ears, nose, and throat; heart; lungs; abdomen; musculoskeletal; extremities; neurological; and lymph nodes.
- Ensure and document that all of the inclusion criteria and none of the exclusion criteria are met.
- Record nonstudy vaccinations as described in [Section 5.8.4](#).
- Ensure that the subject meets none of the temporary delay criteria as described in [Section 4.3](#).
- Confirm understanding of and compliance with protocol requirements for contraception (male subjects only).
- Obtain the subject's investigational product container number using the IRT system. Either blinded site staff or unblinded site staff members may obtain this information.
- Prior to vaccination, collect a blood sample of approximately 25 mL for antibody assessment.

- Prior to vaccination, collect a blood sample of approximately 100 mL for cellular assays (from consenting PBMC subjects at PBMC collection sites only; see [Section 3.1](#)).
- Unblinded site staff member(s) will dispense/administer a 0.5-mL injection of investigational product into the deltoid muscle of the left arm and a 0.5-mL injection of SIV into the deltoid muscle of the right arm (see [Table 6](#)). Please refer to the IP manual for further instructions on this process.

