6.3. RSV Vaccine Month-0, Month-2 Cohort

6.3.1. RSV Vaccine Month-0, Month-2 Cohort, Visit 1: Vaccination 1 (Day 1)

Before enrollment and before any study-related procedures are performed, voluntary, written study-specific informed consent will be obtained from the subject. Each signature on the ICD must be personally dated by the signatory. The investigator or his or her designee will also sign the RSV Vaccine Month-0, Month-2 Cohort ICD. A copy of the signed and dated ICD must be given to the subject. The source data must reflect that the informed consent was obtained before participation in the study.

It is anticipated that the procedures below will be conducted in a stepwise manner. Ensure that the procedures listed prior to administration of the vaccine are conducted prior to vaccination.

- Assign single subject identifier using the IRT system.
- Obtain the subject's demography (including date of birth, sex, race, and ethnicity). The date of birth will be collected to critically evaluate the immune response and safety profile by age.
- Obtain any medical history of clinical significance.
- Assess and record tobacco usage.
- Record all current medications in source documents.
- Perform physical examination including vital signs (weight, height, oral temperature, heart rate, and seated blood pressure), evaluating any clinically significant abnormalities within the following body systems: general appearance; skin; head, eyes, ears, nose, and throat; heart; lungs; abdomen; musculoskeletal; extremities; neurological; and lymph nodes.
- Record nonstudy vaccinations as described in [Section 5.8.4](#).

- Ensure and document that all the inclusion criteria and none of the exclusion criteria are met.
- Ensure that the subject meets none of the temporary delay criteria as described in [Section 4.3](#).
- Confirm understanding of and compliance with protocol requirements for contraception (male subjects only).
- Obtain the subject's randomization number and investigational product container number using the IRT system. Either blinded site staff or unblinded site staff members may obtain this information.
- Prior to vaccination, collect a blood sample of approximately 25 mL for antibody assessment.
- Prior to vaccination, collect a blood sample of approximately 100 mL for cellular assays (from consenting PBMC subjects at PBMC collection sites only; see [Section 3.1](#)).

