- The investigator or appropriately qualified designee reviews the e-diary data online following vaccination to evaluate subject compliance and as part of the ongoing safety review. Daily review is optimal during the active diary period.

6.3.2. RSV Vaccine Month-0, Month-2 Cohort, Visit 2A: 1-Week Follow-up Visit (6 to 8 Days After Visit 1) (*applies to subjects consenting to PBMC collection at PBMC collection sites only*)

- Review the subject's e-diary data.
- Record nonstudy vaccinations as described in [Section 5.8.4](#).
- Confirm understanding of and compliance with protocol requirements for contraception (male subjects only).
- Collect a blood sample of approximately 50 mL for cellular assays.
- Record AEs as described in [Section 8](#).
- Ask the subject to contact the site staff or investigator if a medically attended event (eg, doctor's visit, emergency room visit) or hospitalization occurs.
- Schedule an appointment for the subject to return for the next study visit.

- Complete the source documents.
- The investigator or an authorized designee completes the CRFs.

6.3.3. RSV Vaccine Month-0, Month-2 Cohort, Visit 2: 1-Month Follow-up Visit (28 to 35 Days After Visit 1) (*applies to all subjects*)

- Review the subject's e-diary data and collect the e-diary. Collect stop dates of any e-diary events ongoing on the last day that the e-diary was completed and record stop dates in the CRF if required.
- Record nonstudy vaccinations as described in [Section 5.8.4](#).
- Confirm understanding of and compliance with protocol requirements for contraception (male subjects only).
- Collect a blood sample of approximately 25 mL for antibody assessment.
- Collect a blood sample of approximately 50 mL for cellular assays (from consenting PBMC subjects at PBMC collection sites only).
- Record AEs as described in [Section 8](#).
- Complete the source documents.
- The investigator or an authorized designee completes the CRFs.
- Ask the subject to contact the site staff or investigator if a medically attended event (eg, doctor's visit, emergency room visit) or hospitalization occurs.

6.3.4. RSV Vaccine Month-0, Month-2 Cohort, Visit 3: Vaccination 2 Visit (54 to 66 Days After Visit 1) (*applies to all subjects*)

- Record nonstudy vaccinations as described in [Section 5.8.4](#).
- Ensure that the subject meets none of the temporary delay criteria as described in [Section 4.3](#).

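### Month-0, Month-2 Cohort: no inclusion/exclusion review is listed before dose 2, so an exclusion acquired after dose 1 that triggers no stopping rule meets no listed step that withholds the dose

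*Protocol*

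**What the plan says.** Before the second injection, Protocol Section 6.3.4 lists a record of nonstudy vaccinations, the delay check ("Ensure that the subject meets none of the temporary delay criteria as described in" Section 4.3), the male contraception check, and blood samples. Table 3 matches: the row "Confirm eligibility" is marked at Visit 1 only, while the delay row is marked at Visits 1 and 3.

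At Visit 1 of the same cohort, Section 6.3.1 has a separate line: "Ensure and document that all the inclusion criteria and none of the exclusion criteria are met". At the other dose-2 visit in the protocol, Stage 2 Visit 5, Section 6.2.1 has "Ensure and document that all of the inclusion criteria and none of the exclusion criteria are met", and Table 2 carries the row "Review inclusion/exclusion criteria".

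Section 4.3 covers febrile or other acute illness, acute respiratory illness, recent or anticipated vaccines, and one steroid criterion: "Receipt of short-term (<14 days) systemic corticosteroids". Its opening sentence says that "a subject may be vaccinated once the condition(s) has/have resolved and no other exclusion criteria are met". Section 4 asks for the general eligibility review before a subject enters the study and does not ask for a repeat before later doses.

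**The concern.** Eligibility can change in the two months between doses, and dose 1 can itself be the cause. If the only check against the exclusion list comes before dose 1, a site that follows the Visit 3 list exactly can give dose 2 to a subject who would have been turned away at Visit 1. What is at stake is individual safety in people aged 65 to 85, half of whom receive a second CpG-adjuvanted dose. The review is listed at both of the other visits compared here, which suggests an alignment gap rather than a considered omission.

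**Working it through.** The main check is a comparison of listed steps.

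| Step | Month-0/2 Visit 1 (6.3.1, Table 3) | Month-0/2 Visit 3 (6.3.4, Table 3) | Stage 2 Visit 5 (6.2.1, Table 2) |
|---|---|---|---|
| Inclusion/exclusion review | Yes | No | Yes |
| Temporary-delay check | Yes | Yes | Yes |
| Male contraception check | Yes | Yes | Yes |
| Physical examination | Yes | No | Yes |
| Nonstudy vaccine record | Yes | Yes | Yes |

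Text and table agree for Visit 3, so the gap does not come from a broken table. Where both the review and the delay check appear, they are separate lines, so the delay check was not written to stand in for the review.

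**Does Section 4.3 bring the exclusions in?** Its reference to other exclusion criteria applies to a subject who had a temporary condition that has since resolved. A subject with a new bleeding condition and no temporary condition passes the delay check as written.

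**Which acquired exclusions remain?** Short steroid courses and acute illness are caught by 4.3, and male contraception has its own line. Under Section 7.4, a confirmed SAE or Grade 4 reaction in an RSV recipient that is possibly related, or has no other plausible cause, pauses all RSV vaccination. That leaves:
- new autoimmune disease that is nonserious or unrelated (exclusion 9);
- immunodeficiency (exclusion 7);
- immunosuppressive therapy, or a steroid course of 14 days or more (the rest of exclusion 8);
- a bleeding condition (exclusion 11);
- blood products or immunoglobulin (exclusion 10).

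**Exclusion 10 window.** Exclusion 10 looks back 60 days from product administration. The dose interval D is 54 to 66 days (6.3.4). Look-back days falling after Visit 1 = min(60, D).
- D = 54: 54 of 60 days (90%).
- D = 60 to 66: 60 of 60 days (100%).

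The Visit 1 review therefore says little or nothing about this criterion at dose 2.

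**Precision cost of acting.** SAP Section 4.3.2 requires both vaccinations for the evaluable population, so a subject denied dose 2 leaves it. Take all 31 RSV recipients (Table 4) as evaluable with the same standard deviation s. The half-width of the 95% CI for the mean log titer is t(0.975, n−1) × s / √n.
- n = 31: 2.042/5.568 = 0.3668 s.
- n = 30: 2.045/5.477 = 0.3734 s; ratio to n = 31 is 1.018.
- n = 29: 2.048/5.385 = 0.3804 s; ratio to n = 31 is 1.037.

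Losing 1 of 31 (3.2%) or 2 of 31 (6.5%) widens the interval by about 2% or 4%.

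**The case against.** The strongest reply is that the protocol protects these subjects by other routes.
- A possibly related SAE or Grade 4 reaction in an RSV recipient stops RSV dosing until the internal review committee gives guidance (7.4, 7.4.1).
- Severe e-diary reactions require contact and usually a site visit (6.4).
- Related SAEs and severe related AEs go at once to the sponsor's study physician (8.1), and AEs of specific interest are notified within 24 hours (8.4.2).
- AE collection runs unbroken to Visit 4 (8.1.4), and Table 3 marks AE recording at Visit 3.
- Immunosuppressants, blood products and immunoglobulin are prohibited during the study (5.8.2).
- The investigator may withdraw a subject for safety (6.5).

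The stopping rule stands as a full answer for the events it covers, and the point is limited accordingly. The others lower the chance of unnoticed dosing but are reporting duties, prohibitions or discretion; none is a pre-dose check on the individual. In 6.3.4 the AE-recording line follows the injection. Medications are documented at Visit 1 only in Table 3. Unlike Stage 1 Visits 2 (1-month), 3 and 4, no visit in this cohort prompts the site to check the withdrawal criteria.

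It is also fair that Stage 2 is a separately consented stage a year later, so a fresh review is more natural there. That weakens the comparison with Stage 2, but the gap is visible from this cohort's own two visits.

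Finally, copying the line alone would create an ambiguity. Exclusion 6 bars a history of severe adverse reaction to a vaccine without defining severe, while Tables 7 and 8 label Grade 3 reactions severe. Read literally, the line could remove the most reactogenic subjects before dose 2 in a cohort meant to describe dose-2 tolerability (Section 2). This objection is right, and the fix deals with it.

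**Conclusion.** The concern holds, as a minor subject-safety alignment. In this cohort no listed pre-dose step tells the site to withhold dose 2 for an exclusion acquired after dose 1 that does not trigger a stopping rule. It applies to about 62 second injections, 31 of them RSV vaccine. The documents give no rate for acquiring an exclusion between doses, so no probability is claimed. The cohort is exploratory and no primary endpoint is affected.

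A reader might infer more, and the documents do not support it:
- **That a subject with a serious reaction to dose 1 could be re-dosed unchecked.** For an RSV recipient with a possibly related SAE or Grade 4 reaction, the confirmed stopping rule withholds the dose.
- **That the exclusions lapse after Visit 1.** Exclusion 10 is tied to product administration, and 5.8.2 prohibits several of the treatments throughout. What is missing is the check, not the rule.
- **That the gap can be sized by counting exclusions without a Visit 3 step.** The count depends on whether recording steps qualify. Nonstudy vaccines and AEs are both recorded at that visit, and some exclusions (site-staff status, planned blood donation) have little bearing on dose-2 safety.
- **That fever could go unmeasured at Visit 3.** The fever criterion in 4.3 already implies a temperature reading.

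**What to change.** In Section 6.3.4, before vaccination, add the line already used for Stage 2 Visit 5: "Ensure and document that all of the inclusion criteria and none of the exclusion criteria are met". In Table 3, mark "Confirm eligibility" at Visit 3.

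Add one clarification for exclusion 6 at dose 2: an expected Grade 3 e-diary reaction to dose 1 does not by itself bar dose 2; a severe allergic reaction, a Grade 4 reaction or a related SAE does. This keeps the dose-2 tolerability description from losing its most reactogenic subjects.

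The line does not misfire on the criteria most likely to be affected by a first dose or elapsed time: exclusion 4 concerns RSV vaccination before enrollment or nonstudy RSV vaccine, and inclusion 4 uses age at enrollment.

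The cost is one sentence, one table mark, one clarification and a little site time. Some subjects may not receive dose 2, with the small precision loss calculated above.

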6.4. Unscheduled Reactogenicity Visits Following Vaccination

If the subject reports 1 or more of the following, a contact **must** occur as soon as possible between the subject and the investigator, or a medically qualified member of the study site staff, to assess if an unscheduled visit is required.

- redness at the injection site measuring on the left arm >20 measuring device units (>10.0 cm).
- swelling at the injection site measuring on the left arm >20 measuring device units (>10.0 cm).
- any blackening of the skin (necrosis) at the injection site on the left arm.
- any peeling/scaling of the skin (exfoliative dermatitis) at the injection site on the left arm.
- fever $\geq 102.1^{\circ}\text{F}$ ($\geq 39.0^{\circ}\text{C}$).
- severe injection site pain on the left arm.
- severe fatigue.
- severe headache.
- severe nausea.
- severe vomiting.
- severe diarrhea.
- severe muscle pain.
- severe joint pain.

A site visit must be scheduled as soon as possible to assess the extent of the reaction unless:

- The subject is unable to attend the unscheduled visit, or
- The reaction is no longer present at the time of the contact, or
- The subject recorded an incorrect value in the e-diary (confirmation of an e-diary data entry error).

This contact will be recorded in the CRF and in the subject's source documentation.

If the subject is unable to attend the unscheduled visit, any ongoing reactions must be assessed at the next scheduled visit.

The reaction(s) should be assessed by the investigator or a medically qualified member of the site staff such as a study physician or a study nurse, as applicable to the investigator's local practice, who will:

- Measure oral temperature.
- Measure the subject's pulse rate.
- Measure the subject's blood pressure (sitting).
- Measure minimum and maximum diameters of redness on the left arm (if present).
- Measure minimum and maximum diameters of swelling on the left arm (if present).
- Assess any blackening of the skin (necrosis) at the injection site on the left arm.
- Assess any peeling/scaling of the skin (exfoliative dermatitis) at the injection site on the left arm.
- Assess any injection site pain on the left arm that is present in accordance with the reactogenicity grading scale provided in [Section 7.3.2](#).
- Assess for lymphadenopathy associated with any local reaction.
- Assess any systemic events (fatigue, headache, nausea, vomiting, diarrhea, muscle pain, or joint pain) that are present in accordance with the reactogenicity grading scale provided in [Section 7.3.4](#).
- Ask the subject if he/she attended an emergency room visit or was hospitalized.
- For severe pain at the injection site on the left arm associated with an emergency room visit or hospitalization, severe systemic events, associated with an emergency room visit or hospitalization, or any necrosis or exfoliative dermatitis, the investigator must assess these events in accordance with the severity AE grading scale provided in [Section 8](#) for documentation on the AE CRF.
- Complete the source documents.
- The investigator or an authorized designee completes the CRFs.

Subjects will be instructed to contact the site to report any significant illness, medically attended event, or hospitalization that occurs during the study period.

